Main study participants will be tested using real-time PCR testing of swabs, and these data will be used to identify SARS-CoV-2 infection events for primary analysis. Some main study participants may also receive SARS-CoV-2 testing through university testing systems, or through outside providers, and will be asked to report any positive test results to the study team. Any positive SARS-CoV-2 test results for main study participants – based on PCR testing of study swabs or based on other testing systems indicative of acute infection – will trigger

swabbing of contacts in the PCC and enrollment and swabbing of contacts in the CACC. Secondary analyses of vaccine efficacy will include SARS-CoV-2 infection events diagnosed through any testing system – either by PCR testing of study swabs or through outside testing.

The two contact cohorts – the PCC and the CACC – will both be used for analyses of the vaccine effect on secondary transmission, as described below.

The study is “time-driven”, ie, the primary analysis will occur when all participants have completed the 4 months follow-up. The number of primary endpoint infection events that accrue in the study is random and will depend on the level of SARS-CoV-2 incidence in each arm.

Table 6-1 Study Analysis Sets and Definitions

Analysis Set	Definition	Analyses
Full Analysis Set (FAS)	Main Study participants who enroll in the study	Primary efficacy analyses*
Day 29 Negative (D29-) Set	Participants in the FAS without PCR-confirmed infection on or before Day 29 ⁹	Primary efficacy analyses*
Per-Protocol (PP) Set	Participants in the D29- set who received all planned immunizations at the designated immunization visits within specific visit windows	Secondary efficacy analyses*
Day 29 Negative Transmission Set (D29-TS)	Participants in the D29- set and their contacts in the Prospective and Case Ascertained Contact Cohorts	Primary analyses of secondary transmission*
Case-Cohort Immunogenicity Set (ccIS)	Subset of the FAS that is randomly sampled for measurement of immunological markers and fully described in study SAP	Immunology marker analyses

*These analysis sets include participants without regard to baseline SARS-CoV-2 status. However, primary

efficacy analyses will condition on baseline SARS-CoV-2 seronegative status.

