Determination of eligibility, taking into account all inclusion and exclusion criteria, must be made within 56 days prior to enrollment unless otherwise noted below.

7.1 Inclusion criteria for Main Cohort, Immediate Vaccination Group and Standard of Care Group

General and Demographic Criteria

1. **Age** of 18 through 29 years.
2. **Willingness to be followed** for the planned duration of the study.
3. **Agrees to allow study staff to access school SARS-CoV-2 testing data and outcomes, if applicable.**
4. Ability and willingness to provide **informed consent**.
5. **Assessment of understanding:** volunteer demonstrates understanding of this study; completes a questionnaire with demonstration of understanding of all questionnaire items answered incorrectly.
6. **Willing to be randomized to either immediate vaccination or standard of care group and comply with planned study procedures.**
7. **Agrees not to enroll in another study** of an investigational research agent until the end of the study.
8. **Access to device and internet** for completion of study procedures.

7.2 Exclusion criteria for Main Cohort, Immediate Vaccination Group and Standard of Care Group

General

1. **Acutely ill 72 hours prior to or at screening.** Volunteers meeting this criterion may be rescheduled within the relevant window periods. Participants with minor illnesses can be enrolled at the discretion of the investigator.
2. **Blood products**, systemic immunoglobulins, or monoclonal antibodies (including against SARS-CoV-2) received within 90 days before first vaccination.
3. **Investigational research agents** received within 30 days before first vaccination.
4. **Self-reported known history of SARS-CoV-2 infection.**

Vaccines and other Injections

5. **Prefers to receive COVID-19 vaccination immediately.** (These volunteers to be referred to community resources for vaccination).
6. **Prior administration of a coronavirus** (SARS-CoV-2, SARS-CoV, MERS-CoV) vaccine or current/planned simultaneous participation in another interventional study to prevent or treat COVID-19.

Immune System

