9.3 Enrollment and vaccination visits for Main Cohort, Immediate Vaccination Group

Once a volunteer has consented to trial participation and is found to meet all eligibility criteria (see Sections 7.1 and 7.2), the CRS requests the randomization assignment via a Web-based randomization system. **Enrollment is simultaneous with randomization.** In general, the time interval between randomization and completion of all study activities for Visit 2 should not exceed approximately 7 working days. However, circumstances may require a participant's visit to be changed. This may exceed the 7-day randomization time limit recommendation.

At vaccination visits, the following procedures are performed **before vaccination**:

- COVID-19 symptom check, both vaccination visits
- Specimen collection (**only at first vaccination** visit, see [Appendix E](#))

Following completion of all procedures in the preceding list, and if results indicate that vaccination may proceed, vaccination is prepared and administered per Moderna EUA Fact Sheet and Full Prescribing Information for Vaccination Providers that can be accessed at <https://www.modernatx.com/covid19vaccine-eua/>).

Additionally, the participants will be:

- Reminded to enter information in eDiary throughout the study
- Provided with a supply of nasal swabs and shown how to swab both nostrils

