RCT Enrolled, by arm	Not Vaccine Declined participant type and enrolled Sources: Participant Type CRF, Screening Outcome CRF	1. Immediate randomized, 2. SoC randomized	Yes
Vaccine Declined Enrolled	Enrolled Sources: Screening Outcome CRF	Vaccine Declined	Yes

Disposition(s)	Definition/Data Source	Group(s)	CONSORT diagram
Retrospectively determined ineligible, Not between 18-29 years old	Calculated age at enrollment (enr. date-DOB) is not 18-26 (v1-3) or 18-29 (v4) Sources: Screening Outcome CRF, Demographics e-Diary	1. Immediate enrolled, 2. SoC enrolled, 3. Vaccine Declined enrolled	Yes
Retrospectively determined ineligible, Prior COVID vaccine	Outside vaccination date ² <= enrollment date Sources: Screening Outcome CRF, Outside vaccination CRF	1. Immediate enrolled, 2. SoC enrolled, 3. Vaccine Declined enrolled	Yes
Retrospectively determined ineligible	Not between 18-26/18-29 years old OR prior COVID vaccine See the previous two rows	1. Immediate enrolled, 2. SoC enrolled, 3. Vaccine Declined enrolled	Yes
FAS	Between 18-26/19-29 years old AND no prior COVID vaccine See the previous row (this is a complement)	1. Immediate enrolled, 2. SoC enrolled, 3. Vaccine Declined enrolled	Yes
Without PCR, With study PCR	Participant without vs. with study PCR Source: Study PCR lab data	1. Immediate FAS, 2. SoC FAS, 3. Vaccine Declined FAS	Yes
Baseline SARS-CoV-2 seropositive	Baseline seropositive Source: Serostatus lab data	1. Immediate FAS with study PCR, 2. SoC FAS with study PCR, 3. Vaccine Declined FAS with study PCR	Yes
No qualifying serostatus at baseline	Baseline serostatus unknown among qualifying ³ samples Source: Serostatus lab data	1. Immediate FAS with study PCR, 2. SoC FAS with study PCR,	Yes

Disposition(s)	Definition/Data Source	Group(s)	CONSORT diagram
		3. Vaccine Declined FAS with study PCR	
Baseline SARS-CoV-2 seronegative and PCR positive	Baseline seronegative AND baseline PCR positive Sources: Study PCR and serostatus lab data	1. Immediate FAS with study PCR, 2. SoC FAS with study PCR, 3. Vaccine Declined FAS with study PCR	Yes
Baseline PCR and seronegative	Baseline PCR negative AND baseline seronegative Sources: Study PCR and serostatus lab data	1. Immediate FAS with study PCR, 2. SoC FAS with study PCR, 3. Vaccine Declined FAS with study PCR	Yes

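### The FAS row of SAP 5.1 prints the version-4 age range as 19-29 instead of 18-29; programmed as printed, it would drop eligible 18-year-olds from every efficacy set

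*SAP*

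**What the plan says.** Three rows of the SAP 5.1 disposition table set the age limits. The age row marks a participant retrospectively ineligible if age at enrolment "is not 18-26 (v1-3) or 18-29 (v4"). The combined row reads "Not between 18-26/18-29 years old OR prior COVID vaccine". The FAS row then reads "Between 18-26/19-29 years old AND no prior COVID vaccine", and its source note says "See the previous row (this is a complement").

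Protocol 7.1 gives the age criterion for the randomised groups as "of 18 through 29 years", and Protocol 7.3 gives the same range for the Vaccine Declined Group. The text definition of the FAS in SAP 3.1 requires that participants meet the inclusion criteria and enrol; it gives no age figure. Protocol Table 6-1 defines the FAS more simply as "Main Study participants who enroll in the study".

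For vaccination, SAP 5.1 scores a prior COVID vaccine when the outside vaccination date is "<= enrollment date". Protocol 7.2 and 7.4 exclude prior receipt of a coronavirus vaccine and do not say how a dose on the enrolment day is classed. Protocol 9.3 states "Enrollment is simultaneous with randomization", and SAP section 6 equates enrolment with randomisation for the randomised arms.

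**The concern.** The FAS row is an operative definition. FAS-P is drawn from the FAS, and the table builds the Baseline SARS-CoV-2 negative set from FAS participants with study PCR. A wrong limit here carries into the primary, supportive and descriptive efficacy analyses. A programmer can follow the printed range or the complement note, and the two give different primary populations in a study that SAP 2.5 already calls underpowered.

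The same-day vaccination rule raises a smaller question. Because the trial is open-label, a Standard of Care participant can learn the assignment and be vaccinated elsewhere later that day. That person was eligible when randomised, but the rule classes the dose as prior. Protocol section 8 treats a dose as on-study or outside according to the visit windows of the participant's own group. A study dose on Day 1 therefore keeps an Immediate participant in the set, while a Day 1 dose in Standard of Care is outside and removes the participant.

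**Working it through.** **Age: set check.** The plan gives no count or power figure that depends on this row, so the check is logical. Take each whole-year age, apply the ineligibility row and the FAS row, and see who falls in neither or in both.

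| Protocol version | Ineligible by age | FAS range applied | In neither | In both |
|---|---|---|---|---|
| 1-3 | under 18 or over 26 | 18-26 (as printed) | none | none |
| 4 | under 18 or over 29 | 19-29 (as printed) | age 18 | none |
| 4 | under 18 or over 29 | 18-29 (complement) | none | none |

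The printed row fails as a complement at one age, under one protocol version.

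**Age: possible size.** The documents give neither the age distribution nor the share enrolled under version 4, so both are assumptions here. Let p be the fraction of version-4 enrolees aged 18 and s the fraction of all participants enrolled under version 4. The fraction lost on a literal reading is f = p × s. If events fall in proportion, the width of the log hazard ratio interval grows by the factor 1/√(1 − f).

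- Row applied as the complement: f = 0, no change.
- Ages uniform over 18-29, so p = 1/12 = 8.3%, and s = 1: 1/√(1 − 0.0833) = 1.044, or 4.4% wider.
- Same p with s = 0.5: f = 4.2%, and 1/√(1 − 0.0417) = 1.022, or 2.2% wider.
- p from 2% to 20% with s = 1: 1/√0.98 = 1.010 to 1/√0.80 = 1.118, or 1.0% to 11.8% wider.

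**Same-day rule: where it acts.** Consider a Standard of Care participant with an outside dose on the enrolment day.

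- Primary analysis (SAP 7.2): outside vaccination censoring stops follow-up at the last negative PCR before the dose. A participant vaccinated on the enrolment day would contribute essentially no person-time even if kept.
- ITT-censored analyses (SAP 7.2.1 and 7.2.2): follow-up in Standard of Care continues past outside vaccination, so exclusion removes all of it. If vaccination protects, the remaining comparator is less vaccinated than the randomised one, which by itself would raise the VE estimate. The people removed may also differ in risk, so the net direction is not certain.
- Outside-vaccination counts in SAP 5.1: Standard of Care uptake is understated by the number removed.

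The documents do not give that number.

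**The case against.** A reader might infer that eligible randomised participants are in fact being removed by age. The documents do not show this. The complement note points to 18-29, both ineligibility rows say 18-29, and SAP 3.1 has no 19-year limit. The likeliest explanation is a typing slip that the row's own note resolves. This stands: loss occurs only if the printed range was programmed. It is also fair that 8.3% cannot be read as a share of the trial, because it assumes uniform ages and applies to version 4 only.

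A reader might also infer that the same-day rule contradicts the SAP's ineligibility row. It cannot: it is that row, and the FAS row inherits it. Nor is it a plain breach of the protocol, which is silent on a dose dated on the enrolment day. SAP 5.1 uses only a date, which cannot order the dose against randomisation, so on-or-before is a defensible tie-break. The rule is applied identically to all three groups, and an Immediate participant with an outside dose that day is removed too. Protocol 7.2 excludes volunteers who want vaccination at once, which makes the scenario less common. What survives is the asymmetry between study and outside doses on Day 1, and the fact that some of these doses may follow randomisation.

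Finally, Table 6-1 keeps everyone who enrols, which might suggest that the whole retrospective exclusion is an error. SAP 3.1 states its eligibility restriction openly, in a plan revised after early stopping, so the difference is declared.

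**Conclusion.** The age limit in the FAS row is wrong by one year for version 4. It conflicts with two rows of the same table, with its own note and with the protocol. The consequence is conditional: zero participants if the row is derived as the complement; every version-4 18-year-old if it is programmed as printed. Under uniform ages that is up to about 8% of version-4 enrolees, and correspondingly less of the whole trial if some enrolled under versions 1-3. On the age point the expected harm is lost precision and an ambiguous population; no differential effect between the randomised arms is shown.

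The same-day rule is a smaller and separate matter. It is wider than the protocol's wording and can turn a post-randomisation dose into an ineligibility in Standard of Care. Its effect is confined to the supportive and exploratory ITT-censored analyses and the outside-vaccination counts, and its size is unknown. The documents do not support a claim of bias in the primary analysis from this rule.

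**What to change.** 1. In SAP 5.1, change the FAS row to 18-26 (v1-3) / 18-29 (v4), and derive it in code as the complement of the combined ineligibility row. Confirm that FAS plus ineligible equals enrolled in each group. The cost is a one-digit edit and, if the printed range was used, a rerun of the set derivation.

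2. For at least the ITT-censored analyses in SAP 7.2.1 and 7.2.2, keep randomised participants whose only evidence of prior vaccination is an outside dose dated on the enrolment day, and treat that dose as outside vaccination. Alternatively, report the number of such participants by arm and show the results with and without them. The downside is that a few doses given just before randomisation that day may be kept.

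3. While this row is open, reconcile footnote 2 of the table with SAP 3.2.4. The footnote attaches the imputed first outside dose date to the prior-vaccine row, whereas 3.2.4 says the imputed date is not used for exclusions.

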6. BASELINE DATA

The following baseline characteristics will be summarized by enrollment group for FAS participants: sex, gender (participants with multiple choices reported multiple times), race (participants reporting multiple races reported as 'Multiple'), ethnicity, age (calculated from the date of birth to enrollment, where enrollment is defined as randomized for the RCT arms and the enrollment date on the Screening CRF for the observational arm), residence, number of roommates (0, 1 and >1), number of people in shared communal space (0, 1, 2 and >2), in-person on-campus class attendance (CRF categories), in-person work, volunteer, or on-campus study time (CRF categories), fraternity/sorority membership, current participation in any in-person team sport, sitting inside a bar, restaurant, café or cafeteria (last 2 wks), usual frequency of alcohol consumption (last 2 wks) (CRF categories), usual number of alcohol drinks when consuming (last 2 wks) (CRF categories), potential exposure to a contact with SARS (CRF flags for 1. someone with a recent positive test, 2. someone with possible symptoms, but no diagnosis or test, 3. third party notification system and 4. no contact according to the participant's knowledge), frequency of wearing mask when around other people inside (last 2 wks) (CRF categories), frequency of physical distancing from others when leaving home (last 2 wks) (CRF categories), frequency of meeting in a group 10+ when leaving home (last 2 wks) (CRF categories), frequency of encountering other people not wearing masks when leaving home (last 2 wks) (CRF categories). The Immediate Vaccination arm will be labelled as "Immediate", the Standard of Care arm as "Standard of Care" and the observational (Vaccine Declined) arm as "Observational". Separate summary tables will be created for FAS and SARS-CoV-2 negative participants.

7. PRIMARY EFFICACY/EFFECTIVENESS ANALYSES

Time to event definitions

Except where specified, time is defined as calendar time as opposed to study time. The event occurs at the time of specimen collection for the first study swab positive for SARS-CoV-2.

7.1 Descriptive analysis

Tables

The following table will be used to describe SARS-CoV-2 incidence by group and vaccine receipt. It will be produced first including only baseline SARS-CoV-2 negative participants, and then again including all FAS-P participants. Each participant's incident exposure period will start from either the first nasal swab (if the first swab result was negative) or 90 days after the first swab (if first swab positive). The participant's exposure will be broken down to unvaccinated, one-dose and two-dose exposure periods. The unvaccinated exposure period will include days and events up to (and including) the date of the first study vaccination or censoring, whichever occurs first. The one-dose exposure period will include days and events starting the day after the first vaccine and ending on the date of the second vaccine or censoring, whichever occurs first. The two-dose exposure period will include days starting the day after the second vaccine. The 95% confidence interval for the incidence rate will be calculated using the exact method.

Group	Exposure: number of study vaccine doses	Censoring	Number of incident infections	Person- years	Incidence rate (95% CI)
Immediate arm	Unvaccinated	Outside vaccination		See note 1	
	Unvaccinated	ITT		See note 1	
	Single dose	Outside vaccination		See note 2	
	Single dose	ITT		See note 2	
	Two doses	Outside vaccination		See note 3	
	Two doses	ITT		See note 3	
SoC arm	Unvaccinated	Outside vaccination		See note 4	
	Unvaccinated	ITT		See note 4	
Vaccine Declined arm	Unvaccinated	Outside vaccination		See note 4	
	Unvaccinated	ITT		See note 4	

Note 1: Total number of person-years from the incident follow-up start to the first of study vaccination, infection or censoring.

Note 2: Total number of person-years from the last of incident follow-up start and first dose to the first of second dose, infection or censoring.

Note 3: Total number of person-years from the last of incident follow-up start and second dose to the first of infection or censoring.

Note 4: Total number of person-years from the incident follow-up start to the first of infection or censoring.

Incident follow-up start = either the first nasal swab (if the first swab result was negative) or 90 days after the first swab (if first swab positive)

We will also tabulate counts of SARS-CoV-2 infection events by calendar month (of the first positive nasal swab), arm and presence of symptoms (present vs. absent vs. unknown - see section 9.4).

Plots

Plots of monthly incidence of infection by calendar time (calendar month) by study group will be displayed. Versions with and without the Vaccine Declined group will be created. Months at the beginning and/or end of study may be combined if the total follow-up in them is small. The 95% confidence interval for the incidence rate will be calculated using the exact method.

Kaplan-Meier curves will be used to display cumulative incidence of infection across study groups by study time (time since first PCR). Multiple sets of plots will be produced, corresponding to different 'treatment' of the SoC and Vaccine Declined groups:

1. One set of curves (a curve for each enrollment group) with outside vaccination censoring. Endpoints are otherwise defined as they are for each primary or secondary outcome.
2. One curve for Immediate arm and another curve for SoC arm, censoring at outside vaccination

7.2 Primary efficacy analysis

Objective: To evaluate the effect of mRNA-1273 vaccination on acquisition of SARS-CoV-2 infection

Endpoint: Incident infection by study PCR subject to Outside Vaccination Censoring.

Data sets: Baseline SARS-CoV-2 negative participants enrolled as randomized

Exposure: Randomization, and number of study vaccine doses received within the Immediate Vaccination group

Adjustment covariates: Baseline factors: Age, sex, race/ethnicity, place of residence, attributes from the Baseline SARS-CoV-2 Infection Risk Assessment CRF

Analysis: Vaccine efficacy will be estimated using a time-varying Cox model that stipulates the following hazard function

$$h(t) = h_{0S}(t) \exp \{ \alpha_1 I(T_1 < t) + \alpha_2 I(T_2 < t) + \beta X \}$$

where t is time since study initiation (calendar time), T_1 is the calendar time of the first dose of study vaccine and T_2 is the calendar time of the second dose of study vaccine, $h_{0S}(t)$ is an unspecified baseline hazard that depends on study site, and X is a vector of baseline covariates identified in Section 3.2.5 and 3.2.6 as associated with exposure and/or censoring. The efficacy of one dose of study vaccine will be measured by $1 - e^{\alpha_1}$ and the efficacy of two doses measured by $1 - e^{\alpha_2}$. The model will be fit using the R survival package. Two-sided 95% confidence intervals for the VE estimates will be calculated using the Wald method.

If the set of covariates that is associated with SARS-CoV-2 exposure and/or censoring is too large to permit covariate adjustment, an IPCW analysis will be performed. Specifically, the above Cox model will be fit using a time-dependent weight that corresponds to a (standardized) probability of censoring. The analysis will be implemented using the R ipcswitch package.

